11.4.2. Treatment States

Assessments and events will be classified according to time of occurrence relative to the start and/or stop date of the study treatment.

11.4.2.1. Treatment States for Concomitant Medications Data

Treatment State	Definition
Pre- Treatment	Date < Study Treatment Start Date
On-Treatment	Study Treatment Start Date ≤ Date ≤ Study Treatment Stop Date
Post Treatment	Date > Study Treatment Stop Date

NOTES:

• If the study treatment stop date is missing then the assessment will be considered to be On-Treatment. "On-Study" is considered assessment on-treatment and post-treatment.

11.4.2.2. Treatment States for AE Data

Unless otherwise noted, AE summaries will include both On-Treatment and Post-Treatment AEs.

Treatment State	Definition
Pre-Treatment	AE Start Date < Study Treatment Start Date
On-Treatment	If AE onset date is on or after treatment start date & on or before treatment stop date. Study Treatment Start Date ≤ AE Start Date ≤ Study Treatment Stop Date [+ Lag Time]
Post-Treatment	If AE onset date is after the treatment stop date. AE Start Date > Study Treatment Stop Date
Onset Time Since 1st Dose (Days)	If Treatment Start Date > AE Onset Date = AE Onset Date - Treatment Start Date If Treatment Start Date ≤ AE Onset Date = AE Onset Date - Treatment Start Date +1 Missing otherwise.
Drug-related	If relationship is marked 'YES' on InForm OR value is missing

NOTES:

• If the study treatment stop date is missing then the AE will be considered to be On-Treatment.

11.5. Appendix 5: Data Display Standards & Handling Conventions

11.5.1. Study Treatment & Sub-group Display Descriptors

	Treatment Group Descriptions			
RandAll NG		Data Displays for Reporting		
Code	Description	Description	Order [1]	
A	15 mg FBE IV DNX BID +75 mg OSV BID	15 mg DNX +OSV	2	
B	50 mg FBE IV DNX BID + 75 mg OSV BID	50 mg DNX +OSV	3	
C	IV DNX placebo BID + 75 mg OSV BID	PBO + OSV	1	

NOTES:

1. Order represents treatments being presented in TFL, as appropriate.

11.5.2. Baseline Definition & Derivations

11.5.2.1. Baseline Definitions

Parameter		nts Considered As eline	Baseline Used in Data	
	Screening	Day 1	Display	
Vital Signs (temperature, HR, BP, respiratory rate, oxygen status, ventilation status)	Х	Х	Day 1	
12 Lead ECG	Х	Х	Day 1	
Laboratory parameters	Х	X	Day 1	
Nasopharyngeal Swab		X	Day 1	
Nasal Swab	Х	X	Day 1	
Nasal SAM strips (biomarkers)		X	Day 1	
Nasal wash biomarker		X	Day 1	
BAL biomarkers		Х	Day 1	
Serum Biomarkers		X	Day 1	
Katz ADL		X	Day 1	
Flu PRO		X	Day 1	

For all endpoints (unless stated otherwise) the baseline value will be the latest pre-dose assessment. This is generally expected to be from the Day 1 visit, although such values may be missing or unscheduled assessments may be performed before treatment start.

11.5.2.2. Derivations and Handling of Missing Baseline Data

Definition	Reporting Details
Change from Baseline	= Post-Dose Visit Value – Baseline
% Change from Baseline	= 100 x [(Post-Dose Visit Value – Baseline) / Baseline]
Maximum Change from Baseline	= Calculate the change from baseline at each given timepoint and determine the maximum change

NOTES:

- Unless otherwise specified, the baseline definitions specified in Section 11.5.2.1 Baseline Definitions will be used for derivations for endpoints / parameters and indicated on summaries and listings.
- Unless otherwise stated, if baseline data is missing no derivation will be performed and will be set to missing.

11.5.3. Reporting Process & Standards

Reporting Process			
Software	Software		
The currently support to the currently su	The currently supported versions of SAS and TSCG software will be used.		
Reporting Area			
HARP Server	: US1SALX00259		
HARP Area	: \ARPROD\GSK1325756\MID201023\Final_xx		
QC Spreadsheet : \ARWORK\GSK1325756\MID201023\Final_xx\documents			
Analysis Datasets			

Reporting Process

- Final analysis and IDMC datasets will be created based on Integrated Data Standards Library (IDSL).
- RTF files will be generated for final analysis.

Reporting Standards

General

- The current GSK Integrated Data Standards Library (IDSL) will be applied for reporting, unless otherwise stated:
 - 4.03 to 4.23: General Principles
 - 5.01 to 5.08: Principles Related to Data Listings
 - o 6.01 to 6.11: Principles Related to Summary Tables
 - 7.01 to 7.13: Principles Related to Graphics

Formats

- GSK IDSL Statistical Principles (5.03 & 6.06.3) for decimal places (DP's) will be adopted for reporting of data based on the raw data collected.
- Numeric data will be reported at the precision collected on the eCRF.
- The reported precision from non eCRF sources will follow the IDSL statistical principles but may be adjusted to a clinically interpretable number of DP's.

Planned and Actual Time

- Reporting for tables, figures and formal statistical analyses :
 - Planned time relative to dosing will be used in figures, summaries, statistical analyses and calculation of any derived parameters, unless otherwise stated.
- Reporting for Data Listings:
 - Planned and actual time relative to study drug dosing will be shown in listings (Refer to IDSL Statistical Principle 5.05.1).
 - Unscheduled or unplanned readings will be presented within the subject's listings.
 - Visits outside the protocol defined time-windows (i.e. recorded as protocol deviations) will be included in listings but omitted from figures, summaries and statistical analyses.

Unscheduled Visits

- Unscheduled visits will not be included in summary tables or figures, unless otherwise stated.
 - Unscheduled visits will be included in the maximum toxicity or maximum change from baseline for toxicity tables.
- All unscheduled visits will be included in listings.

Descriptive Summary Statistics		
Continuous Data	Refer to IDSL Statistical Principle 6.06.1	
Categorical Data	N, n, frequency, %	
Reporting of Pharmacokinetic Concentration Data		
Descriptive	Refer to IDSL Statistical Principle 6.06.1	
Summary Statistics	Assign zero to NQ values (Refer to GUI_51487 for further details)	
Reporting of Pharmacokinetic Parameters		
Descriptive	N, n, geometric mean, 95% CI of geometric mean, standard deviation (SD)	

Reporting Standards		
Summary Statistics	of logged data and between geometric coefficient of variation (CVb (%)) will	
(Log Transformed)	be reported.	
	○ CV_b (%) = $\sqrt{(exp(SD^2) - 1) * 100}$	
	(SD = SD of log transformed data)	
Graphical Displays		
Refer to IDSL Statistical Principals 7.01 to 7.13		

11.6. Appendix 6: Derived and Transformed Data

11.6.1. General

Multiple Measurements at One Time Point

- Mean of the measurements will be calculated and used in any derivation of summary statistics but if listed, all data will be presented.
- If there are two values within a visit the value closest to the planned/target day for that visit will be used. If values are the same distance from the target then the mean will be taken.
- Subjects having both High and Low values for Normal Ranges at any post-baseline visits for safety parameters will be counted in both the High and Low categories of "Any visit postbaseline" row of related summary tables. This will also be applicable to relevant Potential Clinical Importance summary tables.

Treatment Start Date

Treatment start date is defined as follows:

 Treatment start date is the date entered onto the IP exposure CRF for when study treatment started.

Study Day

- Calculated as the number of days from initial study treatment start date :
 - Ref Date = Missing → Study Day = Missing
 - Ref Date < Treatment Start Date → Study Day = Ref Date Treatment Start Date
 - Ref Data ≥ Treatment Start Date → Study Day = Ref Date (Treatment Start Date) + 1

Note that Treatment Start Date is considered to be on Study Day 1 and the day before this is Study Day -1; i.e., there is no Study Day 0.

Post-baseline

Post-baseline refers to the combined time periods of On-treatment and Post-treatment.

11.6.2. Study Population

Demographics

Age

- Age, in whole years, will be calculated with respect to the subject's Screening visit.
- GSK standard IDSL algorithms will be used for calculating age where birth date.
- Birth date will be presented in listings as 'YYYY'.

Demographics

Completely missing dates of birth will remain as missing, with no imputation applied.
 Consequently, the age of the subject will not be calculated and will remain missing.

Body Mass Index (BMI)

If not already provided, BMI will be calculated as Weight (kg) / [Height (m)]²

Extent of Exposure

- Number of days of exposure to study drug will be calculated based on the formula:
 - Duration of Exposure in Days = Treatment Stop Date (Treatment Start Date) + 1
- Subjects who were randomized but did not report a treatment start date will be categorised as having zero days of exposure.
- The cumulative dose will be based on the formula:

Cumulative Dose = Sum of (Number of Days x Total Daily Dose)

If there are any treatment breaks during the study, exposure data will be adjusted accordingly.

11.6.3. Safety

ECG Parameters

RR Interval

- IF RR interval (msec) is not provided directly, then RR can be derived as:
 - [1] If QTcB is machine read & QTcF is not provided, then :

$$RR = \left[\left(\frac{QT}{QTcB} \right)^2 \right] * 1000$$

[2] If QTcF is machine read and QTcB is not provided, then:

$$RR = \left[\left(\frac{QT}{QTcF} \right)^3 \right] * 1000$$

 If ECGs are manually read, the RR value preceding the measurement QT interval should be a collected value THEN do not derive.

Corrected QT Intervals

- Machine-read values of RR, QTcB or QTcF should not be replaced with re-derived values
- When not entered directly in the eCRF, corrected QT intervals by Bazett's (QTcB) and Fredericia's (QTcF) formulas will be calculated, in msec, depending on the availability of other measurements.
- IF RR interval (msec) is provided then missing QTcB and/or QTcF will be derived as:

$$QTcB = \frac{QT}{\sqrt{\frac{RR}{1000}}}$$

$$QTcF = \frac{QT}{3\sqrt{\frac{RR}{1000}}}$$

Laboratory Parameters

- Influenza Virus load data from Viroclinics will be imputed as following:
- LLOQ and LLOD per subtype are dependent on the data, assume the values are x.xx,
 y.yy, z.zz, and w.ww for LLOQ, LLOD for qPCR A and q PCR B, respectively

ECG Parameters

- qPCR A: LLOQ=: x.xx log vp/ml, LLOD: y.yy log vp/ml
 - When CT neg (i.e. qPCRA<LLOD), impute y.yy 0.01
 - When qPCRA between LLOD and LLOQ, impute x.xx 0.01
 - When qualitative results are derived from qPCR: when CT is positive value then "Virus detected" and when CT is neg then "Virus not detected".
- qPCR B: LLOQ: z.zz log vp/ml, LLOD:w.ww log vp/ml
 - When CT neg (i.e. qPCRB <LLOD), impute w.ww 0.01.
 - When qPCRB between LLOD and LLOQ, impute z.zz 0.01
 - When qualitative results are derived from qPCR: when CT is positive value then "Virus detected" and when CT is neg then "Virus not detected".
- TCID50: LLOQ = 0.75
 - \circ When <0.75 impute 0.75 0.01 = 0.74.
 - When qualitative results are derived from TCID50: when TCID50 <0.75 impute "No Virus Isolated", when >0.75 impute "Virus Isolated".
- For other laboratory values, if laboratory value which is expected to have a numeric value for summary purposes, has a non-detectable level reported in the database, where the numeric value is missing, but typically a character value starting with '<x' or '>x' (or indicated as less than x or greater than x in the comment field) is present, the number of significant digits in the observed values will be used to determine how much to add or subtract in order to impute the corresponding numeric value. If a character value starting with "<=x", then the numeric value will be x.
 - \circ Example 1: 2 Significant Digits = '< x ' becomes x 0.01
 - Example 2: 1 Significant Digit = '> x' or '>=x' becomes x + 0.1
 - Example 3: 0 Significant Digits = '< x' becomes x 1

11.6.4. Efficacy

Time to Clinical Response (TTCR)

TTCR will be derived as detailed in Section 7.1.2 The following is further considerations for the derivation of TTCR

- If an assessment time is missing the following times will be used in the calculation of TTCR: 8:00, 14:00, 20:00 respectively for morning, afternoon and evening assessments. The imputation will not be done for the study day 1.
- If the subject was discharged but is missing the date of discharge then the latest day from individual components will be used. If subject was discharged but the time of discharge is missing, 12:00 time will be used.
- If the subject withdraws consent on the same day as hospital discharge, TTCR will not be considered a failure.

- Deaths which occur after clinical response will not be considered a failure
- When a subject met vital sign criteria and was discharged from hospital during the 24 hour period of stability confirmation, the time of achieving TTCR was defined as the initial time at which vital signs were resolved and not the time of hospital discharge.
- If the clinical response has not been achieved by study completion, TTCR will be censored at the last assessment date of vital signs.
- If the subject did not achieve a clinical response the reason for censoring will be summarized (i.e. did not achieve vital sign resolution or reason for prematurely discontinuing the study).

Time to Respiratory Response (TTRR)

- Time to Respiratory Response defined as the first time meeting below, for at least 24 hours:
 - o Return to pre-morbid oxygen requirement (subjects with chronic oxygen use), OR
 - Need for supplemental oxygen (administered by any modality ventilator, noninvasive ventilation, facemask, facetent, nasal canula, etc) to no need for supplemental oxygen, OR
 - Respiratory rate >24/min and no supplement oxygen at baseline, and post baseline respiratory rate ≤24/min (without supplemental oxygen)
- Subjects who meet the above criteria at baseline (i.e., normal respiratory response) will not be included in the Kaplan Meier analysis and these subject not be considered as "improved" in the response rate
- If the symptoms have not resolved at Day 45, it will be censored at Day 45.

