Table 4 Time and Events Table: Post-Treatment and Post-Discharge Assessments

Procedures	Post-Discharge Visits/TCs and Assessments Outpatient ^a					
	PT Day 3 (Visit)	Study Day 8 (TC)	Study Day 15 (TC)	Study Day 22 (TC)	Study Day 30 (TC)	Study Day 45 (Visit)
Safety/Efficacy Assessments						
Adverse events	X	X	X	X	X	X
Concomitant medications	X	X	X	X	X	X
Brief Physical Exam	X					X
Complications of influenza / associated antibiotic use ^b	X	X	X	X	X	X
Temperature	X	X	X	X	X	X
Other Vital signs (HR, BP, respiratory rate, oxygen saturation, ventilation status) ^c	X					X
Flu PRO ^d	Daily through Day 14	Daily through Day 14	X	X	X	X
Katz Activities of Daily Living ^e	X	X	X	X	X	X
Activity level ^f	Daily through Day 14	Daily through Day 14	X	X	X	X
Laboratory Assessments						
Clinical chemistry including LFTs ^g (Local+Central)	X					X
Serum Creatinine ^h (Local+Central)	X					X
Hematology ⁱ (Local+Central)	X					X
Pregnancy test ^j	X					
Nasopharyngeal swabs	X					
Exploratory Biomarkers (Blood Sample) ^k	X					X
Transcriptomics (blood sample) ^l	X					X
Nasal SAM strips (biomarkers) ^m	X					X
Nasal washes ⁿ	X					X
Hospital Readmission Status	X	X	X	X	X	X

a. Following discharge from hospital, outpatient clinic visit/TC schedule of assessments will be followed for those patients who are discharged before Day 45. For 5 days treatment, PT Day 3 will be the same as Day 8 and will be a clinic visit.

- b. Complications of influenza such as bacterial pneumonia, pneumothorax, pleural effusion, ARDS, myositis, encephalitis, myocarditis, and associated antibiotic use will be recorded on all assessment days.
- c. Vital signs and ventilation status will be assessed at clinic visits (PT Day 3 and Day 45).
- d. FLU PRO to be measured once daily through Study Day 14.
- e. Activities of Daily Living (Katz Scale) to be done at clinic visits and at TCs.
- f. Activity level assessed by reporting on a 3 point scale of bed rest (1), limited ambulation (2) or unrestricted (3) to be done daily through Study Day 14.
- g. Clinical chemistry including LFTs to be required once every other day until PT Day 3 (for LFTs, local testing for subject management until PT Day 3; central testing for all assessments, including at Day 45).
- h. Serum creatinine required once every day until PT Day 3 (local testing for subject management until PT Day 3; central testing for all assessments, including at Day 45).

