7.3.1. Primary Endpoint

The primary endpoint is time to clinical response (TTCR) ([Table 5](#)).

Clinical response is defined as resolution of at least 4 of the 5 signs described below within the respective resolution criteria, maintained for at least 24 hours, or hospital discharge, whichever comes first.

Table 5 Criteria for Time to Clinical Response

Sign of clinical response	Response criteria
Hospital discharge	Subjects who are discharged from hospital will be considered to have met the clinical response endpoint at the time of hospital discharge and are not required to have documented resolution of at least 4 response criteria (i.e. achieved success at the time of discharge if not observed prior to it).
OR	
Temperature ¹	≤36.6°C (≤97.9°F) – axilla, or ≤37.2°C (≤99°F) – oral, or ≤37.7°C (≤99.9°F) – rectal/core ⁵ , tympanic
AND	
Oxygen saturation ^{2,3}	≥95% (without supplemental oxygen)
AND 2 out of the following 3 criteria:	
Respiratory status	
 Return to pre-morbid oxygen requirement (subjects with chronic oxygen use), OR Need for supplemental oxygen (administered by any modality – ventilator, non-invasive ventilation, facemask, facemask, nasal canula, etc) to no need for supplemental oxygen, OR Respiratory rate ≤24/min (without supplemental oxygen)
Heart rate	≤100/min
Systolic blood pressure ⁴	≥90 mmHg

- Without the use of antipyretics within 8 hours
- A subject with a history of chronic hypoxia (without supplemental oxygen) will satisfy normalization criteria for oxygen saturation if the value (without supplemental oxygen) is ≤2% from subject's historical oxygen saturation baseline as recorded within 12 months prior to enrolment as documented in the subject's medical records.
- This requirement will be waived for subjects with a history of chronic supplemental oxygen requirement who have a baseline oxygen saturation <95% with supplemental oxygen, within 12 months prior to enrolment as documented in the subject's medical records.
- Without inotropic support administered within 2 hours.
- Core temperatures include measurements via a temporal artery thermometer, indwelling catheters and Swan Ganz catheters.

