7.3.2. Secondary Efficacy Endpoints

- Time to Respiratory Response (TTRR): TTRR is defined as meeting at least one criterion below:
 - Return to pre-morbid oxygen requirement (subjects with chronic oxygen use or ventilator support), OR
 - Return to no requirement of supplemental oxygen, OR
 - Respiratory rate ≤24/min (without supplemental oxygen)

- Clinical measures of influenza illness will be evaluated as follows:
 - Time to absence of fever
 - Time to improved oxygen saturation
 - Time to improved heart rate
 - Time to improved SBP
 - Proportion of subjects with clinical response over time
 - Proportion of subjects with improved respiratory status over time
 - Time to improvement of ventilation status: modality and duration of invasive and non-invasive ventilator support, duration of oxygen supplementation.
 - Length of stay in the ICU
 - Frequency of ICU admission and readmission
 - Length of stay in the hospital
 - Rates of development of septic shock
 - Frequency of associated antibiotic use
 - Proportion of subjects with improvement in Ordinal scale of clinical efficacy over time:
 - Death
 - Mechanical vent
 - In the ICU
 - Non-ICU hospitalization
 - Hospital discharge

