2.2. Study Objective(s) and Endpoint(s)

	Objectives	Endpoints
Pri	mary	•
•	To assess the efficacy of treatment with IV DNX twice daily given with oral oseltamivir compared to oral oseltamivir twice daily on time to clinical response (TTCR)	Time to Clinical Response (composite) Hospital discharge OR Normalization of: - Temperature; and - Oxygen status; and - Respiratory status/Heart Rate/SBP(normalization of 2 out of these 3 parameters)
Sec	condary	
•	To assess the efficacy of treatment with IV DNX twice daily given with oral	Time to Respiratory Response defined as meeting at least one criterion below
	oseltamivir compared to oral oseltamivir twice daily on time to respiratory response (TTRR)	Return to pre-morbid oxygen requirement (subjects with chronic oxygen use), OR
		Return to no requirement of supplemental oxygen, OR
		Respiratory rate ≤24/min (without supplemental oxygen)
•	To evaluate clinical measures of influenza illness following treatment with IV DNX twice daily given with oral oseltamivir compared to oral oseltamivir twice daily	Time to absence of fever
		Time to improved oxygen status
		Time to improved heart rate
		Time to improved SBP
		Proportion of subjects with clinical response over time
		Proportion of subjects with improved respiratory status over time
		Time to improvement of ventilation status: modality, frequencies and durations of invasive and non-invasive ventilator support, duration of oxygen supplementation.
		Length of stay in the ICU
		Frequency of ICU admission and readmission
		Length of stay in the hospital
		Rates of development of septic shock
		Frequency of antibiotic use

	Objectives	Endpoints
		Proportion of subjects with improvement in Ordinal scale of clinical efficacy over time: Death Mechanical vent In the ICU/ non MV Non-ICU hospitalization Hospital discharge
•	To characterize the safety and tolerability of IV DNX twice daily given with oral oseltamivir compared to oral oseltamivir twice daily	Frequency of adverse events (AEs) and serious adverse events (SAEs) Frequency of adverse events of special interest (AESIs) Change from baseline in clinical laboratory
•	To characterize the pharmacokinetics of IV DNX in subjects hospitalized for influenza	evaluations, and ECG parameters Standard pharmacokinetic parameters for IV DNX (i.e. AUC, Cmax, Cavg).
Ex	ploratory	

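### The SAP adds an undeclared 24-hour hold to time to respiratory response and does not say whether discharge confirms it, so a responder sent home within a day could be censored at Day 45

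*SAP*

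**What the plan says.** Three places define TTRR, in two ways.

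- Protocol 7.3.2: "TTRR is defined as meeting at least one criterion below". No duration is attached. The objectives table in Protocol Section 3 agrees.
- SAP 2.2: "Time to Respiratory Response defined as meeting at least one criterion below". Again there is no duration.
- SAP 11.6.4: "Time to Respiratory Response defined as the first time meeting below, for at least 24 hours".

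The only censoring rule given for TTRR is also in SAP 11.6.4: "If the symptoms have not resolved at Day 45, it will be censored at Day 45".

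The primary endpoint has a 24-hour requirement too, but there it is tied to discharge. Protocol 7.3.1 requires resolution to be "maintained for at least 24 hours, or hospital discharge, whichever comes first". SAP 7.1.2 lets discharge for clinical improvement stand as the confirmation. SAP 11.6.4 covers the case "When a subject met vital sign criteria and was discharged from hospital during the 24 hour period of stability confirmation" by dating the event at first resolution. SAP 7.1.2 also gives TTCR a 22-hour confirmation window and a rule for missing assessments, and it censors unconfirmed subjects at the last vital-signs date. None of this is stated for TTRR.

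SAP 2.1, which lists changes to the protocol's analysis plan, says only that the analysis is descriptive and reduced.

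**The concern.** Coming off oxygen and leaving hospital can fall close together. If a 24-hour hold is required and discharge cannot confirm it, the in-hospital readings stop before the hold can be shown. The one censoring rule available would then carry a recovered subject to Day 45 as a non-responder. The same subject could have a TTCR event in the first days and no respiratory response for the whole study.

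Protocol 4.4 calls TTRR a key efficacy endpoint because the drug is expected to act mainly in the lung. SAP 8.1.1 names it as the one secondary efficacy endpoint to be summarized. TTRR is also the vertical axis of Figures 6.3, 6.5, 6.7 and 6.9, each with a regression line per treatment group. A value of 45 there, if plotted, would have great influence. SAP Section 1 says that final-analysis decisions are made before unblinding, so a choice between two derivations should not be left to programming.

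**Working it through.** The plan gives no figure to reproduce here, so the check is on timing and on how far one subject can move a summary.

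**1. Can a next-day discharge show 24 hours in hospital?** Protocol 7.3.3 schedules three respiratory readings a day between about 8 AM and 8 PM. SAP 11.6.4 uses 8:00, 14:00 and 20:00 when a TTCR assessment time is missing, and I take those as the grid. Discharge times are assumed. Hours observed = (24 − hour first met) + hour of discharge next day.

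| First met | Out 10:00 | Out 12:00 | Out 14:00 | Out 16:00 |
|---|---|---|---|---|
| 8:00 | 26 | 28 | 30 | 32 |
| 14:00 | 20 | 22 | 24 | 26 |
| 20:00 | 14 | 16 | 18 | 20 |

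A criterion first met in the evening cannot show 24 hours, or even 22, before any of these discharges. One first met at 14:00 fails 24 hours if the subject leaves at noon or earlier. A subject discharged on the same day always fails.

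**2. When is the next scheduled respiratory reading?** After discharge, Protocol Table 4 takes vital signs other than temperature, and ventilation status, only at PT Day 3 and Day 45. Assume the last dose is on the day of discharge or Day 5, whichever is earlier, so that PT Day 3 = last-dose day + 3.

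- Discharge on Day 2, 3 or 4: next reading on Day 5, 6 or 7.
- Discharge on Day 5, 6 or 7: next reading on Day 8.
- Discharge on Day 8 or later: next reading on Day 45.

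A later reading therefore exists in the schedule. The SAP does not say whether it may confirm the hold.

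**3. What does one recoded subject do?** Ten subjects at 2:2:1 give expected arms of 10 × 2/5 = 4, 4, and 10 × 1/5 = 2. One recoded subject moves a response proportion by 1/4 = 25 points or 1/2 = 50 points. If the influenza-positive population is smaller than ten, the step is larger in any arm that loses a subject.

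For the median, take an arm of four with assumed responses on Days 2, 3, 4 and 6. With four at risk and any censoring only at Day 45, the Kaplan-Meier curve reaches 1/2 at the second event.

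- All four count as events: median Day 3, response 4/4.
- The Day 2 or Day 3 subject is recoded: second event on Day 4, response 3/4.
- The Day 4 or Day 6 subject is recoded: second event still on Day 3, response 3/4.
- The Day 2 and Day 3 subjects are both recoded: second event on Day 6, response 2/4.
- The Day 2, 3 and 4 subjects are all recoded: median not reached, response 1/4.

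Recoding always lowers the response proportion. Whether it moves the median depends on which subject is affected.

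**The case against.** The strongest reply is that no rule actually scores these subjects as failures. The Day 45 rule applies to symptoms that have not resolved, and a subject sent home off oxygen has arguably resolved. The rule that imputes missing assessments as non-response is written for TTCR and is not extended to TTRR. Two of the three TTRR criteria concern oxygen need, and Protocol 7.3.3 records oxygen supplementation and method of support with dates and times. SAP Listings 34 and 35 will show them. A recorded stop with no restart could support 24 hours off oxygen without three readings a day. Telephone contacts ask about complications and readmission, so a relapse would probably surface. The gap is widest for the respiratory-rate criterion, which has no start and stop record.

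This stands as far as it goes. A reader might infer that the SAP requires non-response for early discharges, and the text does not say that. But it does not say the opposite either, and two programmers could derive different results for the same subject.

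A reader might also infer that the rule penalizes the fastest recoverers. The documents do not support that. What matters is the gap between meeting the criterion and discharge: a subject weaned late and sent home 12 hours later is equally exposed. Those discharged before Day 8 also get the sooner confirming visit.

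Finally, the study stopped at 10 subjects, nothing is tested, and each subject's TTRR is plotted (Figure 2.2) and listed. An odd case would be visible. That limits the weight of the point without removing it.

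**Conclusion.** The point holds as an undeclared change of definition with a missing confirmation rule. The SAP contradicts itself between 2.2 and 11.6.4, departs from Protocol 7.3.2, and does not say how the hold is confirmed for a subject who leaves inside it. Under the strict reading, such a subject could become a Day 45 censoring. Under a reading that accepts oxygen stop times or a clinic visit, the subject need not.

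The documents do not give the size. The 25 to 50 point step rests on the expected 4, 4 and 2 split, and the median illustration on assumed response days. A reader might put a general figure on the shift. With an exponential true median of 4 days and a fraction p never confirmed, F = 0.5/(1 − p) and the median is 4 × log2(1/(1 − F)): 5.7 days at p = 20% and 10.3 days at p = 40%. The arithmetic is right, but the 4 days, the exponential shape and p have no source in the documents, and every unconfirmed subject is taken as a permanent non-responder. These figures are not an estimate of bias in this trial. No difference between arms has been shown either.

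It should be fixed because the remedy is cheap and the endpoint is the one SAP 8.1.1 selects for summary.

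**What to change.** Bring Protocol 7.3.2, SAP 2.2 and SAP 11.6.4 into line, in one of two ways.

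1. Drop the hold from SAP 11.6.4. This restores the protocol definition and removes the problem.
2. Keep the hold, declare it in SAP 2.1, correct SAP 2.2, and add to SAP 11.6.4 under TTRR: *A discharge for clinical improvement that occurs while a TTRR criterion is met counts as confirmation of the 24-hour hold; the event is dated at the first time that criterion was met.* State also whether the 22-hour window applies, and whether oxygen stop times or post-discharge visits may confirm the hold.

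The cost is a few sentences and a line of programming. Discharge date and time are already collected (Protocol 7.3.3), and SAP Listing 36 includes the reason. The second option has a small downside: a subject who relapses soon after discharge counts as a responder, which the TTCR rule already accepts.
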